15.7 SAMPLE SIZE JUSTIFICATION

A sample size of at least 30 subjects is planned for this study. This is a single arm study and as such, the sample size is not statistically powered for the evaluation of a specific hypothesis, but rather is deemed sufficient to provide meaningful information for evaluation of the specified endpoints and will allow for an informed comparison to existing literature on microwave ablation results. The study will continue to enroll subjects until at least 30 subjects have completed the 3-month visit.

15.8 ANALYSES TO BE CONDUCTED

15.8.1 Disposition of Study Subjects

Subject disposition will be summarized using counts and percentages. The number and percentage of subjects consented, included in each analysis set, completed and discontinued will be tabulated along with the specific reasons for discontinuation.

15.8.2 Demographic and Baseline Characteristics

Summary statistics will be provided for patient demographics and pre-operative surgical characteristics for the Full Analysis Set. Medical and surgical history will be summarized with counts and percentages and summary statistics will also be provided for key baseline laboratory measurements as well as baseline ECOG, Child-Pugh, ASA, and VAS pain scores.

15.8.3 Primary and Secondary Endpoint Analyses

The number and percentage of subjects achieving Technical Success, defined as complete tumor ablation with adequate or insufficient ablation margin, based on contrast-enhanced MRI and CT scans immediately following the ablation procedure, will be summarized and an exact 95% confidence interval will be estimated. A similar summary will be provided for Primary Technique Efficacy, defined as complete tumor ablation with adequate or insufficient ablation margin, based on contrast-enhanced MRI and CT scans follow-up at 1 month after the ablation procedure.

Local tumor progression rates at 1, 3, 6, 9, 12, 18, 24, 30 and 36 months will be estimated using the Kaplan-Meier method and 95% confidence intervals will be provided. Only subjects providing an observation at the given time point will be included in the analysis. A similar summary will be provided for the 36-month for overall and progression free survival rates.

Summary statistics as appropriate for continuous or categorical measurements will be provided for all other secondary effectiveness parameters.

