Statistical Methods:	
Categorical variables will be summarized descriptively by frequencies and associated percentages. Continuous variables will be summarized descriptively by number of subjects, mean, standard deviation, median, minimum, and maximum. Confidence intervals will also be provided for procedure-related variables.
 
The number and percentage of subjects achieving Technical Success will be summarized and an exact 95% confidence interval will be estimated. A similar summary will be provided for Primary Technique Efficacy, as well as for the primary and secondary efficacy rates as previously defined.
 
Local tumor progression rates at 1, 3, 6, 9, 12, 18, 24, 30 and 36 months will be estimated using the Kaplan-Meier method and 95% confidence intervals will be provided.
 
The number and percentage of subjects experiencing adverse events (AEs) will be summarized at the preferred term level using the Society of Interventional Radiology (SIR) clinical practice guidelines for event categorization.
 
Two analyses of study data are planned. The first will occur after 30 subjects have completed the 3-month visit and is intended to provide an initial estimate of device effectiveness for Technical Success as well as to summarize the peri-operative out to 3-month post-operative safety

	
profile of subjects undergoing microwave ablation. There are no plans to use the results of the first analysis for the purpose of stopping the study early. The second analysis will occur after all subjects have completed study participation.

--	--

Table 1: Schedule of Events

Visit No. Visit	Visit1: Screening	Visit2A Pre-Ablation	Visit2B Ablation	Visit2C Post-Ablation	Visit3 1 month	Visit4 3 months	Visit5 6 months	Visit6 9 months	Visit7 1 year	Visit8 18 months	Visit9 2 years	Visit10 30 months	Visit11 3 years	USV Unscheduled Visit ⁸
Interval Windows	Within 5 weeks before ablation	-2 to 0 days	Day 0= Ablation of index tumor	0 to 4 days	1 month (+/- 14 days) after ablation	3 months (+/-28days) after ablation	6 months (+/-28 days) after ablation	9 months (+/-28 days) after ablation	12 months (+/-28 days) after ablation	18 months (+/-28 days) after ablation	24 months (+/-28 days) after ablation	30 months (+/-56 days) after ablation	36 months (+/-28 days) after ablation	NA
Study Activity														
Informed Consent	X													
Demographic Information	X													
Medical/Surgical History	X													

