More recent studies have continued to demonstrate that microwave ablation is safe and effective for the treatment of liver tumors with low complication rates, high rates of technical success, lower rates of local tumor progression than have historically been reported for RF, and promising disease-free and overall survival rates. Zaidi et al²⁹ treated 53 patients with malignant liver tumors with microwave ablation using a laparoscopic or open approach. Morbidity was 11.3% and technical success was 99.3%. The local recurrence rate was low at 0.7%. Alexander et al³⁰ reported on a 9-year retrospective study of 64 patients who underwent MW ablation for focal hepatic malignancies. Likelihood of local recurrence at 1 year was relatively high compared with other studies and varied by histology (39.8% for HCC to 70.8% for non-CRC metastases). Tumor size did not impact rates of complete ablation or local recurrence. Sun et al³¹ reported the results of treating medium sized HCCs (3-5 cm) with microwave ablation. The technical effectiveness rate was high at 93% and the major complication rate was low at 2.7%. There was one procedure related death from an abscess related septicemia. Overall survival was 89%, 74% and 60% at 1, 2, and 3 years respectively. Eng et al³² reported the results of treating 33 patients with colorectal cancer liver metastases using intraoperative microwave ablation. The local recurrence rate was low at 7.8% and overall survival was 35.2% at 4 years. Ziemlewicz et al³³ reported the first larger series of patients with HCC treated with the Certus 140 ablation system. Seventy-five patients with 107 tumors were treated. The technical success rate was 100% and the local tumor progression rate was

low at 8.2%. Overall survival was 76% at median follow-up of 14 months. Leung et al³⁵ reported outcomes of treating 176 patients with liver malignancies using microwave ablation. The local recurrence rate was low at 7.9% at a median follow-up of 20.5 months. Contrary to other recent studies, tumor size and perivascular location were associated with a higher risk of local recurrence. Finally, Wang et al³⁶ reported a local tumor progression rate of 11.8% and 1-year, 2-year, and 3-year overall survival rates of 98.1%, 87.1% and 78.7%, respectively, for patients with colorectal cancer liver metastases treated with ultrasound-guided percutaneous microwave ablation.

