8.5 REMOVAL OF SUBJECTS FROM STUDY

In accordance with the Declaration of Helsinki and Guideline for ICH and Korean GCP, a subject has the right to withdraw from the study at any time for any reason without prejudice to his/her future medical care by the physician or the institution. Should a subject (or subject's legally authorized guardian/representative) decide to withdraw, all efforts will be made to collect any adverse events they have experienced, if applicable.

Subject participation may be terminated prior to completing the study (i.e., the 3-year follow-up visit) for any of the reasons listed below (reasons that do not fit the categories below will be documented as "other"). Any adverse events which are ongoing at the time of discontinuation must be followed until resolution or until they become stable but ongoing. The relevant electronic Case Report Form (eCRF) pages (Study Exit, Adverse Event) will be completed for all withdrawn subjects and the data will therefore be included in the study database.

Subject Choice:

If a subject chooses to withdraw early from the study, the eCRF study completion page should be completed. When a subject's participation is terminated prior to completing the study, the reason for withdrawal is to be documented on the eCRF and in the source documentation.

Intra-treatment:

The Investigator must withdraw a subject during the procedure for one of the following reasons:

- Intra-treatment event that results in conversion to a surgical procedure or other procedure prior to the start of microwave ablation.

Post-treatment:

The Investigator must withdraw a subject after the procedure for one of the following reasons:

- **Concomitant medication/ procedure:**
 - Chemotherapy or radiation therapy for hepatocellular carcinoma may not be performed for 30 days after the procedure
- **Death:**
 - When possible, the cause of death will be documented.

- **Lost to follow-up:**

All subjects should be encouraged to return for protocol required clinic visits for evaluation during the study follow-up period. If a subject is unable to return for a clinic visit or unable to be contacted by telephone, attempts to contact the subject

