15.8.5 Handling of Missing Data and Dropouts

All summaries will be performed only on subjects undergoing the ablation procedure and only observed data will be summarized. There will be no imputation of data for early terminated subjects or for enrolled subjects who do not provide a measurement at a given visit. Subjects who terminate prior to the 3-month visit will be replaced. Subjects terminating at or after the 3-month visit will not be replaced.

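### Local tumor progression is estimated by plain Kaplan-Meier with no rule for deaths without progression; if those deaths are censored, the rate overstates the share who progress locally, and the observed-only restriction adds a second, opposing problem

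*Combined protocol and SAP*

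**What the plan says.** Section 15.8.3 states that LTP rates at nine time points from 1 to 36 months "will be estimated using the Kaplan-Meier method and 95% confidence intervals will be provided". The Statistical Methods entry of the synopsis repeats this ("estimated using the Kaplan-Meier method and 95% confidence intervals will be provided"). The next sentence of Section 15.8.3 adds a restriction: "Only subjects providing an observation at the given time point will be included in the analysis". OS and PFS at 36 months then receive a similar summary.

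No section gives a censoring rule for LTP, names a competing-risk method, or says whether the LTP rate means a net rate or the share of subjects affected. Death appears in Section 8.5 as a reason for post-treatment withdrawal ("When possible, the cause of death will be documented"), with no analysis rule attached. Section 15.8.5 says "There will be no imputation of data for early terminated subjects" and does not mention death. Section 15.1 defers detail to an SAP to be finalized before database lock.

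Under the note to Table 1 and Section 11.10, subjects treated after a recurrence or a new lesion move to six-monthly reduced follow-up. It may be by phone, and its data list contains no imaging.

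**The concern.** LTP is an event of the index tumor. A single-event Kaplan-Meier analysis has two states, event or censored, and nothing in the plan counts death as LTP. A death without LTP would therefore be censored by default. The estimate then assumes that the deceased subject would have had the same later LTP risk as survivors, and 1-KM describes LTP in a setting without death.

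Death is not rare in this population. Eligibility allows Child-Pugh B, ECOG 0-2 and ASA up to 3 (Section 8.1). The HCC microwave series in Tables 3 and 4 that report 3-year survival range from 51% to 81%. In the cited 3-5 cm series, "Overall survival was 89%, 74% and 60% at 1, 2, and 3 years respectively".

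What is at stake is the meaning of a descriptive estimate. The study tests no hypothesis (Section 15.4), and its sample size is justified partly by comparison with published results (Section 15.7). Several of the LTP figures in Section 4.2 are percentages quoted at a mean or median follow-up. A 36-month 1-KM set beside them without a label invites misreading, to the device's disadvantage.

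**Working it through.** The plan gives no LTP rate or event count, so there is no figure to reproduce. The size of the effect is found from assumed inputs.

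**Inputs.** LTP: 8.2% and 8.8% (the two cited series using this system), 12% (several rows of Tables 3 and 4), 25% (the 3-5 cm series, Table 4). Three-year OS: 51% (Table 3), 60%, 73% and 81% (Table 4).

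**Formula.** Take constant, independent hazards over 36 months, with the same death hazard before and after LTP. Let F be the net LTP that 1-KM targets.

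- a = -ln(1 - F)
- b = -ln(OS)
- Cumulative incidence = a/(a+b) × (1 - exp(-(a+b)))

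**Worked case, F = 25%, OS = 60%.** a = 0.2877, b = 0.5108, a+b = 0.7985, and exp(-(a+b)) = 0.75 × 0.60 = 0.45. Cumulative incidence = 0.2877/0.7985 × 0.55 = 19.8%. The overstatement is 25 - 19.8 = 5.2 points, or 26% relative.

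**Range** (cumulative incidence, with overstatement in points):

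| 1-KM at 36 months | OS 81% | OS 73% | OS 60% | OS 51% |
|---|---|---|---|---|
| 8.8% | 7.9% (0.9) | 7.6% (1.2) | 6.9% (1.9) | 6.4% (2.4) |
| 12% | 10.8% (1.2) | 10.3% (1.7) | 9.4% (2.6) | 8.8% (3.2) |
| 25% | 22.7% (2.3) | 21.6% (3.4) | 19.8% (5.2) | 18.5% (6.5) |

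At 8.2% and OS 81% the gap is 0.8 points. In subjects, the extremes are 30 × 0.008 = 0.2 and 30 × 0.065 = 2.0.

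**Simulation.** 30 subjects on the protocol's visit schedule, 3,000 runs per scenario, deaths censored for Kaplan-Meier. Front-loaded means two thirds of the cumulative LTP hazard falls in the first 12 months.

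| LTP / OS | 1-KM | Aalen-Johansen | Gap, constant | Gap, front-loaded | SD of 1-KM, constant |
|---|---|---|---|---|---|
| 12% / 73% | 12.0% | 10.1% | 1.9 | 1.3 | 6.6 |
| 22% / 57% | 22.0% | 16.5% | 5.5 | 3.9 | 9.1 |
| 25% / 60% | 25.0% | 19.1% | 5.9 | 4.1 | 9.4 |

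The constant-hazard gaps slightly exceed the closed form because a subject can die between onset and the visit that would detect LTP. Over all simulated scenarios with LTP of 12-25%, the SD of 1-KM is about 6 to 9 points, a 95% half-width of roughly 12 to 18 points.

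**The restriction sentence at 36 months.** Dropping subjects who died, while still counting any earlier LTP among those alive, gives about the Kaplan-Meier value: 11.9% at 12%/73% and 25.1% at 25%/60%. If in addition half of the LTP subjects lack a 36-month observation (an assumption), the figures fall to 6.3% and 14.3%. These lie below the cumulative incidences of 10.1% and 19.1%. If the sentence carries over to OS, a subject who died earlier provides no 36-month observation unless the death record counts as one, so a literal reading would leave no deaths in the estimate.

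**The case against.** The strongest reply is that no section says deaths will be censored, so a reader who infers a stated censoring rule goes beyond the text. That is correct. Censoring is the default of the named method, and the promised SAP may settle it.

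Nor does the text support a flat statement that the reported rate will be too high. The restriction sentence, combined with reduced follow-up, can reverse the direction. This limits the claim but does not rescue the plan, because it leaves the estimated quantity less defined.

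A third reply is that 1-KM is a legitimate net measure of local control, so cumulative incidence is partly a choice of estimand. This stands too, but the plan does not label its rate as net.

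The inputs are also open to challenge. Tables 3 and 4 give neither estimator nor time horizon for local progression. If their figures are crude proportions, the gap in the 25%/60% row becomes 6.4 points instead of 5.2, and in the 12%/81% row 1.3 instead of 1.2. The 51% survival figure comes from a retrospective series with tumors up to 7 cm, whereas this trial enrols single tumors of 2-5 cm at BCLC stage A. If LTP itself raises mortality, fewer deaths compete and the gap shrinks.

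Finally, a reader might take LTP to be the main long-term effectiveness result. Section 7.2 lists it among unranked secondary endpoints, beside 36-month PFS and OS. No test, error rate or sample size depends on it.

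**Conclusion.** The point holds in conditional form. The plan names single-event Kaplan-Meier for LTP and gives no handling of death. If deaths without LTP are censored, 1-KM overstates the share of subjects who progress locally. The excess at 36 months is about 1 to 6.5 points (10% to 37% relative) for net LTP of about 8-25% and 3-year OS of 51-81%. This assumes constant hazards and equal mortality before and after LTP.

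The effect is modest, and smaller than the 12 to 18 point half-width at 30 subjects. It still merits correction: the interval shows readers its width but not that it is centred on a different quantity, and in a descriptive study the estimate is the product. The restriction to subjects observed at each time point is a separate defect in the same paragraph. Its direction is not fixed, and a change of estimator alone would leave it in place.

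**What to change.** In Section 15.8.3, the synopsis and the detailed SAP:

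- Estimate LTP at each time point by the Aalen-Johansen cumulative incidence function, with death before LTP as a competing event and 95% confidence intervals.
- Delete the restriction to subjects observed at the time point for LTP, PFS and OS. All Full Analysis Set subjects then contribute until event, competing event (for LTP) or last evaluable assessment, and LTP events that occurred earlier are retained.
- Keep 1-KM for LTP as a secondary display, labelled as a net rate, for comparison with literature that used it.
- Keep Kaplan-Meier for OS and PFS, where death is itself an event (taking PFS in its usual sense of progression or death).

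The cost is a few lines of text and one further standard procedure. No new data are needed, since dates of death and LTP assessments are already collected. The downside is two LTP curves to present and explain.

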8. Adverse Event and SAEs: Subjects will be assessed for safety from day of ablation through the 3-year follow-up. All AEs and SAEs will be reported from the day of the ablation up to 3 months after the ablation procedure. Expected serious adverse device effects (SADE), unexpected serious adverse device effects (USADE), life-threatening events, or events that result in death, and all SAEs with definite, possible, probable or unknown relationship to the study device or study procedure, will be reported from day of the ablation through the 3-year follow-up.
9. Unscheduled visits are only for those which are procedure, device or disease related.

NOTE:

- Subjects who have recurred at the target lesion or progressed with a new lesion following the first ablation, and are treated with any treatment post progression will be followed every 6 months (+/-28 days) from the day of the first ablation as a clinic visit or, if clinic visit is not possible, a phone contact visit (if a clinic visit is not possible). This will be called a "Reduced Follow-Up Schedule."

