11.10 REDUCED FOLLOW-UP VISIT

This visit can be a clinic visit or a phone contact visit which will occur every 6 months (+/-28 days) from the day of the first ablation. The following data will be collected only for subjects who have progressed or recurred following the first ablation and are retreated with any treatment post progression:

- Follow-up post-ablation treatment (if applicable);
- Any additional progression(s)/ recurrence(s);
- Survival status;
- Adverse Events (if applicable). Subjects will be evaluated for all adverse events according to the Investigator's standard of care practice during each follow-up visit. Note that for this study, after Visit 4 (3 months), only expected or unexpected serious adverse device effects, life-threatening events, events that result in death and all SAEs with definite, possible, probable or unknown relationship to the study device or study procedure will be reported to the Sponsor, if applicable;
- QOL questionnaires

For subjects on the Reduced Follow-up schedule 6 monthly visits occur until approximately 3 years post ablation.

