11.11 INDEPENDENT REVIEWER (IR)

An Independent Reviewer, from the site in Korea, will be utilized in this clinical trial in order to

reduce the variability between investigators in assessing the CT images (and as needed, MRI and Ultrasound) and to minimize potential bias. The Independent Reviewer will review all CT scans taken throughout the study (including at screening) using the images stored in the hospital's database and without referring to the radiology imaging report in order to avoid influence in the assessment. All images will be taken in accordance with the hospital's Standard of Care. At baseline, the independent reviewer will confirm the presence of one lesion, and its location, size, and BCLC stage.

According to the standard practice at the site in Korea, the independent review will classify the ablation as:

- complete tumor ablation with adequate margin
- complete tumor ablation with insufficient margin
- incomplete tumor ablation.

This assessment will be done for the scans taken following the ablation procedure (Visit 2, for technical success) and at the 1-month visit (Visit 3, for technical efficacy).

At all post-ablation follow up visits, the central reviewer will assess recurrence of the target lesion, progression, meaning a new lesion(s), or lack thereof. If there is a progression or recurrence, the central reviewer will again assess number of lesions, location, size and BCLC stage.

The assessment by the independent reviewer will only be used for the purpose of statistical analysis while the assessment by the investigators will be used for the treatment of the subjects in the study as well as reported in the analysis.

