12.1.1.12 Reporting Serious Adverse Events

Investigator's Responsibility:

The Investigator is required to complete the AE eCRF for:

- All SAEs experienced by the subject from Visit 2B until the subject completes Visit 4 (3 months after the ablation procedure) or withdraws before Visit 4
- All expected and unexpected serious adverse device effects experienced by the subject, all life-threatening events, event that results in death and all SAEs with definite, probable, possible, or unknown relationship to the study device or study procedure after Visit 4 until the subject completes Visit 11 or withdraws before Visit 11.

All serious adverse events must be reported to the Sponsor by the site within 24 hours after the site becomes aware of the information by entering the data into the AE eCRF. The Investigator must avoid disclosing the subject information, by using the ID code, instead of using name, or home address. In case of death, the Investigator has to report as much information as there is available to the Sponsor, including the death certificate and/ or autopsy report (only when autopsy is performed).

The Investigator must report all expected and unexpected serious adverse device effects, and all life threatening events and events resulting in death to the IRB within the timelines regulated by their IRB procedures.

Sponsor's Responsibility:

The Sponsor will follow MFDS's guideline to report safety events related to the study medical devices with the timeline which is regulated by law.

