15.3 INTERVAL WINDOWS

Subjects are scheduled for 9 post-ablation visits under this protocol. For summarization of selected endpoints at post-ablation time points, the following windows will be defined around each scheduled visit to identify the corresponding measurement to be summarized for that visit:

- Visit 3 – 1 month (± 14 days) post ablation;
- Visit 4 – 3 months (± 28 days) post ablation;
- Visit 5 – 6 months (± 28 days) post ablation;
- Visit 6 – 9 months (± 28 days) post ablation;
- Visit 7 – 12 months (± 28 days) post ablation;
- Visit 8 – 18 months (± 28 days) post ablation;
- Visit 9 – 24 months (± 28 days) post ablation;
- Visit 10 – 30 months (± 56 days) post ablation; and
- Visit 11 – 36 months (± 28 days) post ablation.

In cases where multiple measurements fall into a given window, the measurement that is closest in time (number of days) to the scheduled measurement will be utilized in all analyses. Subject and site compliance with the protocol specified visit windows will be monitored throughout the study and the final SAP may be revised to expand the windows as necessary so as not to exclude relevant subject measurements that may be near the existing windows.

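### Section 15.8.3 names Kaplan-Meier for local tumor progression, then restricts each time point to subjects observed at it; the two conflict as written, and no censoring rule is given.

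*Combined protocol and SAP*

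**What the plan says.** Section 15.8.3 gives Kaplan-Meier estimates with 95% confidence intervals for LTP at 1, 3, 6, 9, 12, 18, 24, 30 and 36 months. The next sentence reads: "Only subjects providing an observation at the given time point will be included in the analysis". The one after it reads: "A similar summary will be provided for the 36-month for overall and progression free survival rates". The Statistical Methods entry in the synopsis names Kaplan-Meier for the same nine time points without any restriction.

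The nearest text to a definition of an observation concerns visits:

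- Section 15.3 sets windows around each scheduled visit "to identify the corresponding measurement to be summarized for that visit".
- Section 15.8.5 limits summaries to observed data and rules out imputation for subjects who terminate early or "for enrolled subjects who do not provide a measurement at a given visit". It does not mention censoring.

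Follow-up changes after progression. The Table 1 notes move a group to a reduced schedule, beginning "Subjects who have recurred at the target lesion or progressed with a new lesion following the first ablation" and limited to those then treated for it. Section 11.10 makes this a 6-monthly clinic or phone contact. It lists no CT, but it does collect further progressions or recurrences and survival status. Section 11.11 states: "At all post-ablation follow up visits, the central reviewer will assess recurrence of the target lesion". Section 12.1.1.12 has deaths reported through Visit 11 or withdrawal.

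Section 15.1 promises a detailed SAP before database lock. The text supplied contains no censoring rule for any time-to-event endpoint.

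**The concern.** Kaplan-Meier exists to use partial follow-up. A subject scanned clear at month 18 and then lost adds to the risk set up to month 18, and a subject with LTP at month 6 counts as an event in every later estimate. If month 36 uses only subjects observed at month 36, the first subject is discarded and the second may be too. With no censoring left before month 36, the estimate collapses to a simple proportion among a selected group.

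The sentence can be read in several ways, because the text does not say whether an earlier LTP, a phone contact or a recorded death counts as an observation at a later time. The reduced schedule sharpens this: subjects retreated after LTP are among those likely to lack a later scan, and months 3 and 9 do not fall on a 6-monthly grid. If the restriction carries over to survival, a subject who has died cannot attend month 36.

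Section 15.7 intends the results to be compared with published microwave ablation results. Two analysts could follow section 15.8.3 faithfully and report different LTP rates from the same data, and the confidence interval would not show that the difference came from the reading.

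**Working it through.** The plan states no assumed LTP rate, event count or dropout rate, so there is no figure of its own to reproduce. The check has two parts.

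**1. One invented dataset, three answers.** Take 30 subjects:

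- 5 with LTP, at months 3, 6, 12, 12 and 18;
- 8 lost without LTP, last scans at months 6, 6, 12, 12, 18, 18, 24 and 24;
- 17 free of LTP at month 36.

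The numbers at risk at months 3, 6, 12 and 18 are 30, 29, 26 and 22. The 36-month results are:

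- Kaplan-Meier: 1 − (29/30)(28/29)(24/26)(21/22) = 17.8% (plain Greenwood 95% CI 3.6% to 32.0%).
- Earlier LTP kept, but event-free subjects not seen at month 36 dropped: 5/(5 + 17) = 22.7%.
- Only subjects with a scan at month 36, assuming none of the earlier LTP subjects has one: 0/17 = 0%.

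**2. Expected size.** All inputs are assumptions: constant, independent hazards and dropout of 0% to 20% by month 36. LTP percentages and 3-year overall survival (OS) are paired by row from Tables 3 and 4. Those tables give no time point for local progression; treating it as a 36-month rate is a further assumption.

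Each 36-month cumulative hazard is −ln(1 − probability) for LTP and dropout, and −ln(OS) for death. With H their sum and h_L the LTP part:

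- LTP observed first: C = (h_L/H)(1 − e^(−H)).
- Event-free and still in follow-up: E = e^(−H).
- Rate when earlier LTP is kept but other unobserved subjects are dropped: C/(C + E).

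Example with LTP 12%, OS 51%, dropout 10%: H = 0.1278 + 0.6733 + 0.1054 = 0.9065; C = 0.0841; E = 0.4039; rate = 0.0841/0.4880 = 17.2%. About 30 × 0.488 ≈ 15 of 30 subjects would contribute.

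| Assumed LTP | 3-year OS and source | Rate at dropout 0%, 10%, 20% |
|---|---|---|
| 12% | 81% (Table 4, 68 patients, laparoscopic) | 13.2%, 13.9%, 14.6% |
| 12% | 51% (Table 3, 49 microwave patients) | 16.4%, 17.2%, 18.2% |
| 25% | 60% (Table 4, HCC of 3–5 cm) | 30.6%, 31.9%, 33.4% |
| 25% | 73% (Table 3, 26 microwave patients, surgical) | 28.3% to 30.9% across the range |
| 6% | 73% (Table 4, 1,007 patients) | 7.0% to 7.8% across the range |
| 7% | 73% (Table 4, 234 patients) | 8.1% to 9.1% across the range |

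*New-lesion retreatment without a scan.* Suppose event-free subjects retreated for a new lesion are also excluded. At an assumed 30% and 50% by month 36 and no dropout, the first three rows become 15.6% and 18.3%, 19.4% and 22.8%, and 35.1% and 39.9%.

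*Earlier LTP excluded.* Let S(t) be the LTP-free proportion and f the fraction of subjects with LTP by month 30 who are excluded at month 36. Death and dropout are left out here. The rate is N/(N + S(36)), with N = [S(30) − S(36)] + (1 − f)[1 − S(30)]. For 12% it is 9.7% at f = 0.25 and 2.1% at f = 1. For 25% it is 20.8% and 4.7%.

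*Carried forward.* If earlier LTP is carried forward among subjects still in contact, bias is negligible under independence.

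*Overall survival.* If recorded deaths count but dropouts are excluded, 10% and 20% dropout turn OS of 51% into 49.5% and 47.9%, 60% into 58.6% and 57.0%, and 81% into 80.1% and 79.1%. Progression-free survival was not quantified.

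**Simulation.** With 30 subjects on the protocol's visit grid, 10% dropout and 6,000 runs, ordinary Kaplan-Meier averaged 11.9% for a true 12% (OS 51%) and 25.0% for a true 25% (OS 60%). Keeping earlier LTP but dropping other unobserved subjects gave 16.3% and 31.0%, slightly below the closed form because LTP is found only at visits.

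**The case against.** The strongest reply is that the sentence is loosely worded rather than wrong. The synopsis names Kaplan-Meier without a restriction, and section 15.8.5 gives the sentence an ordinary meaning: observed data, no imputation. On that reading there is no bias. A detailed SAP is still due before database lock, and the 36-month results belong to the second analysis under section 15.8.4, so there is time to clarify.

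The illustrations can also be challenged:

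- The row pairing 12% with 51% comes from a study with tumors up to 7 cm and a mean follow-up of 25 months, among earlier studies that section 4.2 describes as using underpowered, non-cooled systems.
- The two largest Table 4 series with 3-year survival give shifts of only about 1 to 2 points.
- The same-device series report local progression of 8.2% and 8.8%, below the rates that show the largest shifts.
- The 30% to 50% retreatment rate has no source in the documents.
- Excluding every earlier LTP is implausible at the 6-monthly times, because the reduced schedule still records recurrences. The Table 1 notes also allow a phone contact only when a clinic visit is not possible.

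Finally, the study is descriptive and small: 7/30 has an exact 95% CI of 9.9% to 42.3%, wider than most of these shifts.

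Much of this stands as a limit on size and severity. It does not remove the conflict. The sentence is a stated inclusion rule, it does not say number at risk or no imputation, and the nearby visit-based text makes the literal reading available. Sampling error is reported in the interval; the choice of reading is not.

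**Conclusion.** The concern holds. Followed as written, section 15.8.3 discards censored follow-up and possibly earlier events, and nothing in the supplied text supplies the missing definitions. Confidence is high that the rule conflicts with the named method. The direction and size of any bias depend on the reading adopted: none under the benign reading; upward by about 1 to 8 points over the table rows when event-free subjects who died or dropped out are excluded; downward when earlier LTP is excluded, with the near-total loss of events a worst case only. These sizes rest on the constant-hazard, independence and dropout assumptions above and are illustrations, not forecasts. LTP is affected, and 36-month progression-free and overall survival are too if the restriction carries over. Technical Success and the 3-month safety analysis are not. This should be fixed, but it does not threaten the primary result.

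**What to change.** Delete the restricting sentence from section 15.8.3. State there and in the SAP that Kaplan-Meier estimates of LTP, progression-free survival and overall survival include all Full Analysis Set subjects, with earlier events retained at every later time point, including for subjects on Reduced Follow-Up. Then define:

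- **LTP:** event at the first scan showing LTP; censored at the last evaluable liver scan.
- **Progression-free survival:** event at the first of target-lesion recurrence, new lesion or death; censored at the last evaluable assessment.
- **Overall survival:** event at death; censored at the last date known alive, using the survival status collected under section 11.10.

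Report numbers at risk at each time point. A cumulative-incidence estimate of LTP with death as a competing event would be a useful addition but is not needed to resolve this point.

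The cost is wording only, with no new data or visits. Reported figures may move in either direction, or not at all if number at risk was what the sentence meant. Settle it before the results are known, so that the reading is not chosen with the rates in view.
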